# 6. INVESTIGATIONAL PLAN

## 6.1. Overall Trial Design

This Phase 2, multi-center, open-label extension trial will provide deramiocel to HOPE-2 trial subjects who completed 12 months of follow-up. The trial will assess the safety and efficacy of deramiocel administered as 20 IV infusions, each separated by 3 months. All subjects will undergo a targeted screening assessment within 30 days prior to first infusion, unless otherwise stated, to confirm eligibility based on protocol inclusion and exclusion criteria.

Administration of deramiocel (Day 1) should occur within a maximum of 30 days following confirmation of eligibility; if a delay of more than 30 days between enrollment and deramiocel administration is unavoidable, a conversation between the Investigator and Medical Monitor should occur to determine the need for repeat screening prior to infusion. For the purposes of this trial, subjects that initiate an infusion at Day 1 and receive any amount of deramiocel are considered enrolled.

A schematic of the trial design is provided in Appendix A and a summary of all assessments is provided in Appendix B.

Subjects will complete trial assessments at Screening; Day 1; Months 3, 6, 9, 12 ( $\pm$ 14 days, each), 15, 18, 21, 24, 27, 30, 33, 36, 39, 42, 45, 48, 51, 54, 57, and 60 ( $\pm$ 21 days, each). Baseline safety and efficacy assessments will be conducted prior to first infusion on Day 1. For subsequent infusions at Months 3, 6, 9, 12, 15, 18, 21, 24, 27, 30, 33, 36, 39, 42, 45, 48, 51, 54, and 57 safety and efficacy assessments will be conducted prior to infusion, unless otherwise specified.

All intravenous infusions will be conducted in an outpatient setting at the investigative site on Day 1 and at Months 3, 6, 9, 12, 15, 18, 21, 24, 27, 30, 33, 36, 39, 42, 45, 48, 51, 54, and 57. Prior to each IP infusion, medication(s) will be administered to the subject as determined by the Investigator based on the pre-treatment guidelines Section 9.7 and/or institutional protocols to minimize the risk of potential severe allergic reactions such as anaphylaxis. Subjects will be observed in the outpatient setting for at least two hours post infusion and then discharged the same day if medically cleared by the site Investigator.

If clinically indicated, an unscheduled in-person visit will be performed at the investigative site with targeted assessments based on presentation of signs and symptoms after any infusion.

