### 6.2.2. Secondary Endpoints

The *secondary safety endpoint* is the incidence and severity of all treatment-emergent adverse events from baseline through Month 60.

The *secondary efficacy endpoints* include the changes from baseline through the Month 60 timepoint for the following:

- Upper body functionality using PUL 2.0 assessment at Months 12, 24, 36, 48, and 60
- Distal-level PUL 2.0 for subgroup of subjects with entry level scores of 2 and 3 at Months 12, 24, 36, 48, and 60
- Mid-level PUL 2.0 for subgroup of subjects with entry level scores of 4 and 5 at Months 12, 24, 36, 48, and 60
- Left Ventricular Ejection Fraction (LVEF) (i.e., Cardiac MRI) measurement at Month 24, 36, 48, and 60
- Left Ventricular End Systolic Volumes-Indexed (ESVI) measurement at Month 24, 36, 48, and 60
- Left Ventricular End Diastolic Volumes-Indexed (EDVI) measurement at Month 24, Month 36, 48, and 60
- Other cardiac parameters, including but not limited to mass, unindexed volumes, cardiac output, wall thickening percentage, and end diastolic and end systolic wall thickness at 24, 36, 48, and 60

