#### 2.2.4 Secondary Efficacy Endpoints

The *secondary efficacy endpoints* include the change from baseline (PUL 2.0: HOPE-2-OLE Baseline, Cardiac MRI: HOPE-2 Screening Baseline) through Month 60 for the following:

- Upper body functionality using the PUL 2.0 assessment (i.e. Upper level PUL:2.0) at Months 24, 36, 48, and 60
- Distal level PUL 2.0 for subgroup of subjects with entry level PUL 2.0 scores of 2 and 3, at Month 12, 24, 36, 48, and 60
  - Entry level at baseline of HOPE-2-OLE
- Mid-level PUL 2.0 for subgroup of subjects with entry level PUL 2.0 scores of 4 and 5, at Month 12, 24, 36, 48, and 60
  - Entry level at baseline of HOPE-2-OLE
- Left Ventricular Ejection Fraction (LVEF (i.e. Cardiac MRI) at Month 24, 36, 48, and 60.
- Left Ventricular End Systolic Volume, Indexed (Cardiac MRI) at Month 24, 36, 48, and 60.
- Left Ventricular End Diastolic Volume, Indexed (Cardiac MRI) at Month 24, 36, 48, and 60
- Other cardiac parameters, including but not limited to mass, unindexed volumes, and end diastolic and end systolic wall thickness at 24, 36, 48, and 60

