# 4.6 Analysis Populations

The following analysis populations will be defined.

Enrolled Population: The enrolled population will include all subjects who signed the informed consent form and/or given assent.

Safety Population: The safety population will be defined as all subjects who received any amount of IP. All analyses will be based on the Safety Population, unless specified otherwise

For all efficacy analyses defined in this document, the Safety Population will be utilized.

Efficacy analyses combining HOPE-2-OLE data with either External Comparator for the PUL 2.0 Combined Total (ECP) or External Comparator for Cardiac (ECC) will use Safety Population for the HOPE-2-OLE subjects, and all subjects provided by ECP or ECC, unless specified otherwise

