# 6.2 Primary Efficacy Endpoint

The primary efficacy endpoint is the change from baseline (Day 1) to Month 12 in the PUL 2.0 Combined Total Score (high-level + mid-level + distal level dimensions). Observed and changefrom-baseline values will be summarized (n, mean, SD, minimum, and maximum). The 95% confidence intervals (CI) for the mean estimates also will be displayed.

To place the change from baseline (Day 1) for the PUL 2.0 Combined Total Score in context of the preceding HOPE-2 study and the Gap Phase, the following observed and change from baseline values, where not already tabulated, will be summarized (n, mean,

SD, minimum, and maximum) along with the 95% confidence intervals (CI) for the mean estimates. Figures will be provided for mean change for the four scenarios below.

- Non-treatment mean change HOPE-2 vs. Gap Phase: Change from the HOPE-2 baseline to Month 12 HOPE-2 [Main Phase] for the subjects in OLE study who were placebo subjects in HOPE-2 study and for these same subjects the change from Month 12 HOPE-2 to baseline (Day 1) HOPE-2-OLE [Gap Phase].
- On-treatment mean change HOPE-2 vs. HOPE-2-OLE:
  - Change from HOPE-2 baseline to Month 12 [Main Phase] for subjects in the OLE study who were deramiocel subjects in HOPE-2 study.
  - Change from HOPE-2-OLE baseline (Day 1) to Month 12 HOPE-2-OLE for subjects in the HOPE-2-OLE study who were on the placebo arm in HOPE-2 study.
- Gap Phase mean change comparison: Change from Month 12 HOPE-2 to baseline (Day 1) HOPE-2-OLE [Gap Phase] for the subjects in the HOPE-2-OLE study who were deramiocel subjects in the HOPE-2 study compared with the subjects in the HOPE-2-OLE study who were placebo subjects in the HOPE-2 study. As a reference, the change from HOPE-2 baseline to HOPE-2 Month 12 for subjects in the HOPE-2-OLE study who were deramiocel subjects in HOPE-2 study will be included.
- Year over year mean change during HOPE-2-OLE: For the safety population of the HOPE-2-OLE each year's change will be compared.
  - Change from HOPE-2-OLE baseline (Day 1) to Month 12 HOPE-2-OLE (Year 1).
  - Change from Month 12 HOPE-2-OLE to Month 24 HOPE-2-OLE (Year 2)
  - Change from Month 24 HOPE-2-OLE to Month 36 HOPE-2-OLE (Year 3)

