# 6.3 Secondary Efficacy Endpoints

The *secondary efficacy endpoints* include the change from baseline (PUL 2.0: HOPE-2-OLE Baseline, Cardiac MRI: HOPE-2 Month 12) through Month 60 for the following:

- Upper body functionality using PUL 2.0 assessment (i.e. Upper level PUL:2.0) at Months 12, 24, 36, 48, and 60
- Distal level PUL 2. at Month 12, 24, 36, 48, and 60
- Mid-level (elbow) PUL 2.0 at Month 12, 24, 36, 48, and 60
- LVEF (i.e. Cardiac MRI) at Month<del>,</del> 24, 36, 48, and 60.
- Left Ventricular End Systolic Volume, Indexed (Cardiac MRI) at Month, 24, 36, 48, and 60.
- Left Ventricular End Diastolic Volume, Indexed (Cardiac MRI) at Month, at Month 24, 36, 48, and 60.
- Other cardiac parameters, including but not limited to mass, unindexed volumes, and end diastolic and end systolic wall thickness at 24, 36, 48, and 60.

Observed values and change from baseline will be summarized (n, mean, SD, minimum, and maximum) for all secondary endpoints. Descriptive statistics for the External Comparators, ECP and ECC (section 6.4) will be presented for comparison with endpoints for which data are available.

Further comparisons will be formally made for the 24- and 36-month visits (if available) utilizing real-world evidence from external sources. The data and methods utilized for these comparisons is described in the next section.

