# 6.4 External Comparators (Exploratory Efficacy Part 1)

For both the ECP and ECC, propensity score matching will first be attempted to produce an appropriate sample of real-world controls for comparison with the treated subjects from HOPE-2 OLE. If propensity score matching is not appropriate due to small sample size or other limiting factors, then cohort matching will be employed next. In either case, baseline characteristics available in both studies (e.g. baseline LVEF/PUL, age, etc.) will be utilized in the matching algorithm. External Comparator analyses will not be performed or reported if cell sizes are not sufficiently large for statistical analyses after either cohort or propensity score matching is performed. This will be determined separately and independently for the ECP and ECC datasets. If matching is not feasible summary level data may be analyzed.

If propensity score matching is feasible, the following parameterization will be utilized. Greedy nearest-neighbor matching using the logit of the propensity score and an appropriate caliper will be utilized to select matches. Up to 5 matches per treated subject will be used, given available data. Caliper width will be selected such that no treated samples are dropped from the analysis, i.e. at least one control subject will be selected per treated subject. Treated subject records will be sorted in ascending order by propensity score probability.

Baseline characteristics of matched subjects juxtaposed with treated subjects will be reported. In the case of propensity score matching, weighted statistics will be utilized including in analysis and modeling where appropriate.

Indexed volumes will be harmonized between studies: the body-surface area calculation utilized in the HOPE-2 study will be applied to the ECC to recalculate indexed volumes.

The HOPE-2 Month 12 visit will be utilized as the HOPE-2-OLE baseline visit for cardiac MRI parameters, as no cardiac MRI measurements were conducted at the HOPE-2-OLE baseline visit.

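### SAP 2.2.4 takes cardiac MRI change from HOPE-2 Screening, while SAP 6.3 and 6.4 take it from HOPE-2 Month 12; the exploratory ECC comparison also leaves its time origin and control baseline-scan rule unstated

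*SAP*

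**What the plan says.** **Protocol.** Section 6.2.2 says the secondary efficacy endpoints "include the changes from baseline through the Month 60 timepoint for the following", and the list includes LVEF, ESVI and EDVI. Section 6.1 says "Baseline safety and efficacy assessments will be conducted prior to first infusion on Day 1". Section 12.2 schedules no trial cardiac MRI before Month 24. The protocol names no MRI baseline visit.

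**SAP, secondary endpoints.**
- Section 2.2.4: "PUL 2.0: HOPE-2-OLE Baseline, Cardiac MRI: HOPE-2 Screening Baseline) through Month 60".
- Section 6.3, for the same endpoints: "PUL 2.0: HOPE-2-OLE Baseline, Cardiac MRI: HOPE-2 Month 12) through Month 60".
- Section 6.4: "The HOPE-2 Month 12 visit will be utilized as the HOPE-2-OLE baseline visit for cardiac MRI parameters". The reason given is that no MRI was done at OLE baseline.
- Section 4.3 has a general rule: baseline is the latest available value before the first OLE dose.
- Section 4.7 forms a subgroup by baseline LVEF above 45% and does not name the scan.

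**SAP, external comparator.** Section 6.3 says "Further comparisons will be formally made for the 24- and 36-month visits (if available) utilizing real-world evidence from external sources". Section 6.4 matches on baseline characteristics such as LVEF and age. It then fits a continuous-time random-slope model and reports the ECC treatment difference at 24 months. Section 6.5 adds an ANCOVA of change to Month 24. Section 4.6 brings into these analyses "all subjects provided by ECP or ECC, unless specified otherwise".

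**The concern.** Sections 2.2.4 and 6.3 define one set of endpoints in nearly the same sentence but name different baseline scans. A programmer working from the endpoint definitions and one working from the analysis section would produce different LVEF, ESVI and EDVI changes at every MRI visit.

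The two scans also differ in treatment status. The OLE includes subjects from both HOPE-2 arms; SAP 6.2, for example, tabulates "Change from HOPE-2 baseline to Month 12 [Main Phase] for subjects in the OLE study who were deramiocel subjects in HOPE-2 study". For those subjects Screening is before treatment and Month 12 is after a year of follow-up on deramiocel. For former placebo subjects both scans precede any deramiocel. In an open-label study of 13 subjects, the choice of scan should be fixed before results are seen.

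The ECC comparison raises a smaller, related question. Treated subjects have two possible time origins about a year apart: OLE Day 1, from which 4.3 counts study days, and HOPE-2 Month 12, which 6.4 calls their MRI baseline visit. The model section ties its time variable to neither. It also does not say which scan serves as baseline for a control who has several.

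**Working it through.** **Inputs from the documents.** SAP 4.1 gives a HOPE-2 Main Phase of 12 months and a gap of about 1 year (taken as 12 months). The protocol places MRI at OLE Months 24, 36, 48 and 60. Neither document gives a rate of LVEF decline.

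**Step 1: intervals under each baseline.** For OLE month m:
- from HOPE-2 Month 12: 12 + m
- from HOPE-2 Screening: at least 12 + 12 + m, because any time from Screening to HOPE-2 baseline adds to it

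| OLE month | From HOPE-2 Month 12 | From HOPE-2 Screening | Interval longer by |
|---|---|---|---|
| 24 | 36 | ≥ 48 | ≥ 33% (48/36) |
| 36 | 48 | ≥ 60 | ≥ 25% (60/48) |
| 48 | 60 | ≥ 72 | ≥ 20% (72/60) |
| 60 | 72 | ≥ 84 | ≥ 17% (84/72) |

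If the gap is assumed to be 9 to 15 months, OLE Month 24 lies 33 to 39 months after HOPE-2 Month 12 and at least 45 to 51 months after Screening.

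**Step 2: size in LVEF points.** Assume, since the documents give no figure, a linear decline of s = 1 to 3 points per year. The two baselines then give changes that differ by at least s × 12/12 = 1 to 3 points at each visit. The difference is smaller if HOPE-2 treatment slowed decline in former deramiocel subjects.

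**Step 3: ECC comparison with no true drug effect.**
- *Reading A.* Change is taken from HOPE-2 Month 12, time is counted from OLE Day 1, and controls are followed 24 months from their baseline scan. Treated change is −s × 36/12 = −3s and control change is −s × 24/12 = −2s. The difference is −s, or −1 to −3 points, against deramiocel. With a 9- to 15-month gap it is −0.75s to −1.25s, or −0.75 to −3.75 points over the same range of s.
- *Reading B.* Time runs from the baseline scan in both groups. At 36 elapsed months the difference is −3s − (−3s) = 0.

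**Step 4: what Reading B implies for timing.** On that clock, 24 months falls at about OLE Month 12 (12 + 12), where SAP 8 says no MRI was collected. OLE Month 24 falls at about 36 months, of which 24/36 = 67% is on OLE dosing (24/39 = 62% to 24/33 = 73% for a 15- to 9-month gap).

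**The case against.** The strongest reply on the baseline is that the intended scan is not in real doubt. Both analysis sections name HOPE-2 Month 12, and 6.4 gives the reason. The general rule in 4.3 also excludes Screening whenever a Month 12 scan exists. This stands: only 2.2.4 is out of line. A reader might infer that every cardiac analysis, including the subgroup above 45% LVEF, has an undetermined baseline. The documents do not support that, since 4.3 and 6.4 both point away from Screening. A cross-reference is still worthwhile, because 4.3 read literally could select a standard-of-care scan from the gap, and Protocol 12.3 provides for collecting such data.

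On the ECC, a reader might infer that controls have no baseline at all, or that the comparison is biased against deramiocel as written. Neither follows. Section 6.4 matches on baseline LVEF and the model has a baseline term, so control baselines are assumed to exist; what is missing is the rule for choosing the scan. The bias in Step 3 arises only under Reading A. Reading B is natural for a continuous-time model whose baseline visit is named as HOPE-2 Month 12, and it carries no such bias. Against that, 6.3 refers to visits and 6.5 to Month 24, which suggest the OLE visit. The text does not settle the matter.

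It is also fair that the consequences are limited. The secondary MRI results are summarised descriptively, SAP 4.5 states that no hypotheses are pre-specified, and the ECC analysis is dropped if matched cells are too small.

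**Conclusion.** The contradiction between 2.2.4 and 6.3/6.4 is in current SAP text and should be corrected; confidence is high. It moves the baseline by at least 12 months, lengthens the intervals by at least 17% to 33%, and changes the treatment status of the baseline scan for former deramiocel subjects. The translation into 1 to 3 LVEF points rests on an assumed rate of decline.

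The ECC point is a gap in specification, held with lower confidence. Its effect ranges from zero to about one year of decline against deramiocel, depending on which clock is used. The primary endpoint, PUL 2.0 at Month 12, is unaffected by either point.

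**What to change.** **Baseline.** In SAP 2.2.4, replace the HOPE-2 Screening baseline with HOPE-2 Month 12 for cardiac MRI. In 4.3 and 4.7, cross-refer to that MRI baseline. This costs a few words and no new data.

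**ECC.** In 6.4 and 6.5:
- measure model time as actual time from the baseline MRI in both groups;
- state the rule that selects each control's baseline scan;
- compare the groups at equal elapsed time.

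This needs SAP wording and minor programming, but it has a real cost. On that clock the stated 24-month contrast has no treated scan near it. Moving to about 36 months, where the OLE Month 24 scans lie, replaces a stated timepoint. About a third of that interval precedes OLE dosing, so any OLE effect is diluted. Precision there depends on ECC scan dates and follow-up, which the documents do not describe; if follow-up is short, the contrast will rest on fewer controls or on extrapolation.

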#### 2.2.5 Exploratory Safety Endpoints

Exploratory safety endpoints include the analysis of the elevation of HLA antibodies against the donor cells (i.e., DSAs) to determine a level considered clinically significant using mean florescence intensity [MFI].

#### 2.2.6 Exploratory Efficacy Endpoints

The exploratory efficacy endpoints include retrospective standard-of-care patient data from HOPE-2 to the beginning of HOPE-2-OLE and/or an external comparator pertaining to the following at appropriate timepoints:

- Upper body functionality (i.e., the PUL 2.0 Combined Total Score)
- Left ventricular Ejection fraction (LVEF) (i.e., cardiac MRI)

# **3** STUDY DESIGN

This Phase 2, multicenter, open-label extension trial will provide deramiocel to subjects who completed 12 months of follow-up in the HOPE-2 trial. The trial will assess the safety and efficacy of deramiocel, administered up to 20 IV infusions, each separated by 3 months. All subjects will undergo a targeted screening assessment within 30 days prior to first infusion, unless otherwise stated, to confirm eligibility based on protocol inclusion and exclusion criteria.

Administration of deramiocel (Day 1) should occur within a maximum of 30 days following confirmation of eligibility; if a delay of more than 30 days between enrollment and deramiocel administration is unavoidable, a conversation between the investigator and medical monitor should occur to determine the need for repeat screening prior to infusion.

Subjects will complete trial assessments at Screening; Day 1; Months 3, 6, 9, 12 ( $\pm$ 14 days, each), 15, 18, 21, 24, 27, 30, 33, 36, 39, 42, 45, 48, 51, 54, 57, and 60 ( $\pm$ 21 days, each). Baseline safety and efficacy assessments will be conducted prior to first infusion on Day 1. For subsequent infusions at Months 3, 6, 9, 12, 15, 18, 21, 24, 27, 30, 33, 36, 39, 42, 45, 48, 51, 54, and 57 safety and efficacy assessments will be conducted prior to infusion, unless otherwise specified.

All IV infusions will be conducted in an outpatient setting at the investigative site on Day 1 and at Months 3, 6, and 9, 12, 15, 18, 21, 24, 27, 30, 33, 36, 39, 42, 45, 48, 51, 54, and 57 trial visits. Prior to each investigational product (IP) infusion, medication(s) will be administered to the subject as determined by the Investigator based on the pre-treatment guidelines and/or institutional protocols to minimize the risk of potential severe allergic reactions, such as anaphylaxis. Subjects will be observed in the outpatient setting for at least 2 hours after infusion and then discharged on the same day if medically cleared by the site Investigator. If clinically indicated, an unscheduled in-person visit will be performed at the investigative site, with targeted assessments based on presentation of signs and symptoms after any infusion.

The schedule of assessments for the study is presented in Section 9.1 (Appendix A).

### 3.1 Sample Size

Thirteen subjects who were enrolled in and completed the 12-month randomized period in the HOPE-2 trial will be enrolled in this trial.

# **3.2 Deramiocel Treatment**

This is not a randomized study. All subjects will receive open-label treatment with deramiocel (150M cardiosphere-derived cells [CDCs]) administered as an IV infusion on Day 1 and at Months 3, 6, and 9, 12, 15, 18, 21, 24, 27, 30, 33, 36, 39, 42, 45, 48, 51, 54, and 57.

### **3.3 Data Safety Monitoring Board**

The Data Safety Monitoring Board (DSMB) will review data and advise Capricor about any safety matters throughout the trial. The objectives, roles, and responsibilities of the DSMB, as well as the format and frequency of meetings, will be documented in the DSMB charter.

### 3.4 Interim Analyses

No formal interim analyses are planned.

# 4 GENERAL STRATEGIES FOR DATA PRESENTATION

Data with qualifiers (e.g., "<") will be listed with the qualifier but will be summarized without the qualifier. Subject data listings will include all data that are collected for all subjects. Listings will be sorted by site, subject number, nominal visit, date, and time (as applicable), unless otherwise indicated.

Categorical analyses will be summarized using counts and percentages. Percentages will be based on the number of subjects in the analysis set for whom there are non-missing data, unless otherwise specified. Continuous variables, including change from baseline, will be summarized using descriptive statistics [n, mean, standard deviation (SD), median, minimum, maximum].

All analyses will be performed using SAS v 9.3 or higher (SAS Institute, Inc, Cary, North Carolina, USA). Validation and quality control of the tables, listings and figures (TLFs) will follow the appropriate Innovative Analytics standard operating procedures (SOPs).

